#### 7.4.2.2. Definition of a SAE

A serious adverse event is any untoward medical occurrence that, at any dose:

- Results in death
- Is life-threatening

NOTE: The term ‘life-threatening’ in the definition of ‘serious’ refers to an event in which the subject was at risk of death at the time of the event. It does not refer to an event, which hypothetically might have caused death, if it were more severe.

- Requires hospitalization or prolongation of existing hospitalization

NOTE: In general, hospitalization signifies that the subject has been detained (usually involving at least an overnight stay) at the hospital or emergency ward for observation and/or treatment that would not have been appropriate in the physician’s office or out-patient setting. Complications that occur during hospitalization are AEs. If a complication prolongs hospitalization or fulfills any other serious criteria, the event is serious. When in doubt as to whether “hospitalization” occurred or was necessary, the AE should be considered serious.

- Hospitalization for elective treatment of a pre-existing condition that did not worsen from baseline is not considered an AE.
- Results in disability/incapacity, or

NOTE: The term disability means a substantial disruption of a person’s ability to conduct normal life functions. This definition is not intended to include experiences of relatively minor medical significance such as uncomplicated headache, nausea, vomiting, diarrhea, influenza, and accidental trauma (e.g. sprained ankle) which may interfere or prevent everyday life functions but do not constitute a substantial disruption.

- Is a congenital anomaly/birth defect.
- Medical or scientific judgement should be exercised in deciding whether reporting is appropriate in other situations, such as important medical events that may not be immediately life-threatening or result in death or hospitalization but may jeopardize the subject or may require medical or surgical intervention to prevent one of the other outcomes listed in the above definition. These should also be considered serious. Examples of such events are invasive or malignant cancers, intensive treatment in an emergency room or at home for allergic bronchospasm, blood dyscrasias or convulsions that do not result in hospitalization, or development of drug dependency or drug abuse.
- Protocol-specific SAEs:
  - All events of possible drug-induced liver injury with hyperbilirubinae defined as ALT  $\geq$  3xULN and bilirubin  $\geq$  2xULN (>35% direct) (or ALT  $\geq$  3xULN and INR>1.5, if INR measured) termed ‘Hy’s Law’ events (INR measurement is not required and the threshold value stated will not apply to patients receiving anticoagulants).
  - **Note:** bilirubin fractionation is performed if testing is available. If testing is unavailable, record presence of detectable urinary bilirubin on dipstick indicating direct bilirubin elevations and suggesting liver injury. If testing is unavailable and a subject meets the criterion of total bilirubin  $\geq$  2xULN, then the event is still reported as an SAE. If INR is obtained, include values on the SAE form. INR elevations >1.5 suggest severe liver injury.
  - Any new primary cancers and treatment emergent malignancies (including squamous cell carcinoma and new primary melanoma) with the exception of basal cell carcinoma (BCC). BCC should be reported as an AE or SAE based on the discretion of the investigator.
  - Symptomatic LVEF decrease that meets stopping criteria or asymptomatic LVEF decrease that does not recover, as outlined as LVEF guidance (Section [5.8.3.1](#)).
  - Retinal pigment epithelial detachment (RPED) or retinal vein occlusion (RVO)

#### **7.4.2.3. Laboratory and Other Safety Assessment Abnormalities Reported as AEs and SAEs**

Any abnormal laboratory test results (hematology, clinical chemistry, or urinalysis) or other safety assessments (e.g., ECGs, radiological scans, vital signs measurements), including those that worsen from baseline, and felt to be clinically significant in the medical and scientific judgement of the investigator are to be recorded as AEs or SAEs, in accordance with the definitions provided.

However, any clinically significant safety assessments that are associated with the underlying disease, unless judged by the investigator to be more severe than expected for the subject’s condition, are not to be reported as AEs or SAEs.

**7.4.2.4. Disease-Related Events and/or Disease-Related Outcomes Not Qualifying as SAEs**

An event which is part of the natural course of the disease under study (i.e., disease progression or hospitalization due to disease progression) does not need to be reported as an SAE. Death due to disease under study is to be recorded on the Death eCRF form. If however, the underlying disease (i.e., progression) is greater than that which would normally be expected for the subject, or if the investigator considers that there was a causal relationship between treatment with study medication(s) or protocol design/procedures and disease progression, then this must be reported as an SAE.

**7.4.2.5. Time Period and Frequency for Detecting AEs and SAEs**

The investigator or site staff is responsible for detecting, documenting, and reporting events that meet the definition of an AE or SAE.

All SAEs and adverse events (AEs) will be collected from the time the first dose of study treatment is administered until 30 days after discontinuation of study treatment regardless of initiation of a new anti-cancer therapy or transfer to hospice.

From the time a subject consents to participate in and completes the study (See Section 4.2), all SAEs assessed as related to study participation (e.g., protocol-mandated procedures, invasive tests, or change in existing therapy), will be reported promptly to Novartis as indicated in Table 23.

After study treatment discontinuation, the investigator will monitor all AEs/SAEs that are ongoing until resolution or stabilization of the event or until the subject is lost to follow-up. At any time after 30 days from the last dose of study treatment, the investigator may report any AE that he/she believes is possibly related to study treatment.

**7.4.2.6. Prompt Reporting of Serious Adverse Events and Other Events to Novartis**

Serious adverse events (SAEs), pregnancies, and liver function abnormalities meeting pre-defined criteria will be reported promptly by the investigator to Novartis as described in [Table 23](#) once the investigator determines that the event meets the protocol-definition for that event.

**Table 23 Time Frames for Reporting SAEs and Other Events**

Type of Event	Initial Reports		Follow-up Information on a Previous Report	
	Time Frame	Documents	Time Frame	Documents
All SAEs	24 hours	SAE data collection tool	24 hours	Updated SAE data collection
Pregnancy	24 hours	Pregnancy notification	2 weeks	Pregnancy follow-up form
Cardiovascular or death event	Initial and follow up reports to be completed within one week of when the cardiovascular event or death is reported	"CV events" and/or "death" data collection tool(s) if applicable	Initial and follow up reports to be completed within one week of when the cardiovascular event or death is reported	Updated "CV events" and/or "death" data collection tool(s) if applicable
Liver Chemistry Abnormalities:				
ALT $\geq$ 3 x ULN PLUS total bilirubin $\geq$ 2 x ULN (> 35% direct) or ALT $\geq$ 3 x ULN and INR > 1.5, if INR measured	24 hours b	SAE data collection tool, liver event eCRF form, and liver imaging and/or biopsy	24 hours	Updated SAE data collection tool and updated liver event eCRF form c
ALT $\geq$ 8 x ULN; ALT $\geq$ 3 x ULN with hepatitis or rash or $\geq$ 3 x ULN but < 5 x ULN that persists $\geq$ 4 weeks	24 hours b	Liver event eCRF form c	24 hours	Updated liver event eCRF form c
ALT $\geq$ 5 x ULN PLUS total bilirubin < 2 x ULN	24 hours b	Liver event eCRF form does not need completing unless elevations persist for 2	24 hours	
ALT $\geq$ 5 x ULN PLUS total bilirubin < 2 x ULN that persists	24 hours b	Liver event eCRF form c	24 hours	Updated liver event eCRF form c
ALT $\geq$ 3 x ULN but < 5 x ULN PLUS total bilirubin < 2 x ULN	24 hours b	Liver event eCRF form does not need completing unless elevations persist for 4 weeks or subject cannot be		

Abbreviations: ALT = alanine transaminase; AST = aspartate aminotransferase; eCRF = electronic case report form; INR = international normalized ratio; SAE = serious adverse event; ULN = upper limit of normal.

- INR measurement is not required; if measured, the threshold value stated will not apply to subjects receiving anticoagulants.
- Novartis to be notified at onset of liver chemistry elevations to discuss subject safety.
- Liver Event Documents (i.e., "Liver Event CRF" and "Liver Imaging CRF" and/or "Liver Biopsy CRF", as applicable) should be completed as soon as possible.

In the event of abdominal pain or suspected pancreatitis, amylase and lipase laboratory samples should be collected.

Liver chemistry stopping, follow-up, and monitoring criteria are provided in [Appendix 7](#). Methods for detecting, recording, evaluating, and following-up on AEs and SAEs and procedures for completing and transmitting SAE reports to Novartis are provided in the SPM.

#### **7.4.2.7. Regulatory reporting requirements for SAEs**

Prompt notification of SAEs by the investigator to Novartis is essential so that legal obligations and ethical responsibilities towards the safety of subjects are met.

Novartis has a legal responsibility to notify both the local regulatory authority and other regulatory agencies about the safety of a product under clinical investigation. Novartis will comply with country-specific regulatory requirements relating to safety reporting to regulatory authorities, Institutional Review Boards (IRB)/Independent Ethics Committees (IEC) and investigators.

Investigator safety reports will be prepared for suspected unexpected serious adverse reactions according to local regulatory requirements and Novartis policy and will be forwarded to investigators as necessary.

An investigator who receives an investigator safety report describing an SAE(s) or other specific safety information (e.g., summary or listing of SAEs) from Novartis will file it with the IB and will notify the IRB/IEC, if appropriate according to local requirements.

### **7.4.3. Pregnancy**

#### **7.4.3.1. Pregnancy Testing and Prevention**

The need for a screening pregnancy test depends on whether a female subject is of childbearing potential or non-childbearing potential.

**A female of non-childbearing potential** (i.e., physiologically incapable of becoming pregnant) is defined as any female who has had a hysterectomy, bilateral oophorectomy (ovariectomy) or bilateral tubal ligation or tubal occlusion, or is post-menopausal.

A practical definition accepts menopause after 1 year without menses with an appropriate clinical profile, e.g., age appropriate, >45 years in the absence of hormone-replacement therapy (HRT). In questionable cases, the subject must have a follicle-stimulating hormone (FSH) value >40 mIU/mL and an estradiol value <40 pg/mL (<140 pmol/L).

**A female of child-bearing potential** is defined as any female who does not meet the criteria of non-childbearing potential as described in the previous paragraph.

Women of childbearing potential must have a negative serum pregnancy test within 14 days prior to enrollment and agree to use effective contraception. Subjects with a positive pregnancy test result must be excluded from the study. Subjects with a negative pregnancy test result must agree to use an effective contraception method as described below throughout the treatment period and until 4 months after the last dose of study treatment.

Novartis acceptable contraceptive methods, when used consistently and in accordance with both the product label and the instructions of the physician, are as follows:

- An intrauterine device with a documented failure rate of less than 1% per year.
- Male partner sterilization prior to the female subject's entry, and this male is the sole sexual partner for that female.
- Complete abstinence from sexual intercourse for 7 days prior to enrollment, throughout the treatment period, and for at least 4 months after the last dose of study treatment. Abstinence is only acceptable when in line with the preferred and usual lifestyle of the subject. Periodic abstinence (e.g. calendar, ovulation, symptothermal, post-ovulation methods, etc) and withdrawal are not acceptable methods of contraception.
- Double-barrier contraception: condom and occlusive cap (diaphragm or cervical/vault caps) with a vaginal spermicidal agent (foam/gel/cream/suppository).

**Note:** Hormonal-based methods (e.g., oral contraceptives) are not permitted due to potential drug-drug interactions with dabrafenib.

Female subjects who are lactating must discontinue prior to first dose of study treatment and must refrain from nursing throughout the treatment period and for 4 months following the last dose of study treatment.

If a subject becomes pregnant during the treatment period of the study, the study treatments should be stopped immediately.

**Note:** French/German subjects: no contraception for men is required

#### **7.4.3.2. Pregnancy Reporting**

Any pregnancy that occurs during study participation must be reported using a clinical trial pregnancy form. To ensure subject safety, each pregnancy must be reported to Novartis within 24 hours of learning of its occurrence. The pregnancy must be followed-up to determine outcome (including premature termination) and status of mother and child. Pregnancy complications and elective terminations for medical reasons must be reported as an AE or SAE. Spontaneous abortions must be reported as an SAE.

Any SAE occurring in association with a pregnancy brought to the investigator's attention after the subject has completed the study and considered by the investigator as possibly related to study treatment, must be promptly reported to Novartis.

In addition, the investigator must attempt to collect pregnancy information on any female partners of male study subjects who become pregnant while the subject is enrolled in the study. Pregnancy information must be reported to Novartis as described above.

#### **7.4.4. Laboratory Assessments**

All protocol-required laboratory assessments must be conducted in accordance with the Central Laboratory Manual and Protocol Time and Events Schedule ([Table 19](#)). If any local laboratory assessments are undertaken during the course of the trial and they result in a change in patient management (for example SAE or AE or dose modification) the assessment data must be recorded in the patients CRF.

Laboratory requisition forms must be completed and samples must be clearly labelled with the subject number, protocol number, site/centre number, and visit date. Details for the preparation and shipment of samples and a list of reference ranges for all safety parameters will be provided by the central laboratory in a separate instruction manual.

Laboratory assessments must be processed through ██████████ Central Laboratories. If an investigator feels that that safety of the patient is jeopardized by waiting for central labs to return, local labs may be drawn in addition to the central lab for treatment purposes. If any additional laboratory assessments are performed at the institution's local laboratory, refer to the SPM for appropriate processing and handling of samples to avoid duplication and/or additional blood draws.

If local laboratory assessments document a need for dose modification/interruption, an AE or an SAE, these assessments should be entered into the eCRF per the eCRF completion guidelines.

Clinical chemistry and haematology parameters to be tested are listed in [Table 24](#). Female subjects will have a serum pregnancy test at Screening; urine pregnancy testing may be done during study treatment, if necessary.

**Table 24 Clinical Chemistry and Hematology Parameters**

Clinical Chemistry Parameters
Albumin
Alkaline Phosphatase
Alanine Transaminase (ALT) or Serum Glutamic Pyruvic Transaminase (SGPT)
Aspartate Aminotransferase (AST) or Serum Glutamic Oxaloacetic Transaminase (SGOT)
Gamma-Glutamyl Transpeptidase (GGT)
Blood Urea Nitrogen (BUN) or urea
Calcium Creatinine c
Glucose (random)
Lactate Dehydrogenase (LDH)
Magnesium
Phosphate
Potassium
Sodium
Total Bilirubin b
Total Protein
Hematology Parameters
White Blood Cell (WBC) Count (absolute)
Absolute neutrophil (ANC) count
Hemoglobin
Hemoglobin A1C
Hematocrit
International Normalized Ratio (INR; at Screening only) a
Platelet Count
Prothrombin Time (PT; at Screening only) a
Partial Thromboplastin Time (PTT; at Screening only) a
Automated WBC Differential (expressed as %):
Basophils
Eosinophils
Lymphocytes
Monocytes
Neutrophils
Other tests

Amylase and lipase [monitor via local laboratory where appropriate to evaluate certain AEs (i.e., abdominal pain, pancreatitis, etc.)]
serum $\beta$ -hCG (human chorionic gonadotrophin)
For subjects with a history of chronic HBV and/or HCV, the following tests will be performed at Screening: 
 
• Viral hepatitis serology;
 
• Hepatitis B surface antigen and Hepatitis B core antibody (IgM); and/or
 
• Hepatitis C RNA
 

- a. Coagulation panel to be done at Screening only.
- b. Bilirubin fractionation is recommended if total bilirubin is  $> 2 \times$  the upper limit of normal (ULN).
- c. If serum creatinine is  $> 1.5$  mg/dL, creatinine clearance should be calculated using the standard Cockcroft-Gault formula [[Appendix 3](#)].

#### 7.4.5. Ophthalmic Examination

Subjects are required to have a standard ophthalmic examination conducted by an ophthalmologist prior to first dose (baseline), week 4 (Month 1), week 24 (Month 6) and annually thereafter unless clinically indicated sooner. Additional ophthalmic examinations will be performed only as symptomatically warranted.

The exam will include visual acuity (best corrected), tonometry (intraocular pressure measurement), visual field examination, slit lamp biomicroscopy of the anterior segment (with special attention to inflammation) and the posterior segment, and indirect fundoscopic examination with special attention to possible retinal abnormalities. Optical coherence tomography is strongly recommended at scheduled visits, and if retinal abnormalities are suspected or noted. Other types of ancillary testing including color fundus photography and fluorescein angiography are also recommended if clinically indicated.

#### 7.4.6. Vital Signs

Vital sign measurements will include systolic and diastolic blood pressure, body temperature, pulse rate, body weight, and height (only at Screening). Body temperature, weight and height measurements should be recorded in the metric scale.

See Section [5.8.3.2.1](#) for details on monitoring of hypertension.

#### 7.4.7. Physical Examinations

Complete physical examination is indicated at screening and discontinuation and will include assessments of eyes, neurological and cardiovascular systems, lungs, abdomen, and any other areas with signs and symptoms of disease, and of the head, neck, ears, nose, mouth, throat, thyroid, lymph nodes, extremities, and a full skin exam to assess cutaneous malignancies and proliferative skin diseases. Dermatologic skin exams may be referred to a Dermatologist, if needed.

If possible, the same physician should perform each examination for the duration of the study to ensure consistency between evaluations (i.e., if the subject is referred to a Dermatologist for the Screening examination, the Dermatologist should do all follow-up dermatologic skin assessments).

Neurological exams should be performed by the Investigator as per the schedule in ([Table 19](#)). Alternatively, subjects may be referred to a Neurologist, at the discretion of

the Investigator.

A thorough neurological assessment is required at baseline focusing on:

- Mental status
- Cranial nerves
- Motor system
- Sensory system
- The deep tendon reflexes
- Coordination and the cerebellum
- Gait

Neurological Symptoms may include the following (but are not limited to):

- Headache
- Nausea and/or vomiting
- Vertigo and/or dizziness
- Restlessness and/or irritability
- Fatigue or sleeplessness
- Hearing loss
- Muscle weakness
- Balance problems
- Speech problems
- Others

#### **7.4.8. Electrocardiograms (ECG)**

Twelve (12)-lead ECGs will be obtained using an ECG machine that automatically calculates heart rate and measures PR, QRS, QT, RR and QTcB intervals.

At each assessment, a single 12-lead ECG will be performed by qualified site personnel after the subject has rested in a semi-recumbent or supine position for at least 5 minutes.

[figure not shown]
[figure not shown]
Two copies of the ECG tracing should be obtained at the time of the ECG; the first copy will be kept in the subject's medical chart and the second copy will be kept in the study file for retrospective collection by the Sponsor if necessary. See Section [5.8.3.3](#) for dose modifications guidelines if QTc prolongation occurs.

#### **7.4.9. Echocardiograms (ECHO)**

Echocardiograms (ECHO) will be performed to assess cardiac ejection fraction. The echocardiographer's evaluation should include an evaluation for left ventricular ejection fraction. Copies of all ECHO scans will be centrally collected for review. Collection details will be AgMedNet Imaging Acquisition Guidelines.

[figure not shown]

#### 7.6.2. BRAF mutation assay

Subjects in ALL cohorts may be enrolled based on certified assay local test results. 

The tissue requirements for the BRAF mutation assay evaluating patient eligibility for the study may be provided in the SPM.

Additional biomarkers related to the activity of dabrafenib and trametinib may also be analyzed as described in Section [7.6](#).

## 8. DATA MANAGEMENT

Data Management will identify and implement the most effective data acquisition and management strategy for each clinical trial protocol and deliver datasets that support the protocol objectives.

For this study, subject data will be entered into the electronic case report forms (eCRFs), transmitted electronically to Novartis (or designee), and be combined with data from other sources in a validated data system.

Clinical data management will be performed in accordance with applicable standards and data cleaning procedures with the objective of resolving errors and inconsistencies in the data which would otherwise impact on the analysis and reporting objectives, or the credibility of the Clinical Study Report. All AEs and concomitant medications terms will be coded using the Medical Dictionary for Regulatory Activities (MedDRA) and a custom medication dictionary.

The eCRFs (including queries and audit trails) will be retained by Novartis, and copies will be sent to the investigator to maintain as the investigator copy.

## 9. DATA ANALYSIS AND STATISTICAL CONSIDERATIONS

### 9.1. Hypotheses

The primary efficacy objective of this study is to assess the intracranial response (IR) rate in BRAF V600E mutation positive subjects assessed by Investigators using modified RECIST 1.1 criteria for Cohort A:

- Cohort A: 75 Subjects who are treatment-naive for brain metastases,

asymptomatic and stable on corticosteroids.

The study is designed to provide evidence to support the null hypothesis,  $H_0$ : IRR  $\leq$  35% or to reject it in favor of the alternative hypothesis,  $H_A$ : IRR  $\geq$  50% for BRAF V600E mutation-positive subjects in Cohort A.

The null hypothesis is based on results of BRF113929 (BREAK-MB), a study of dabrafenib in two cohorts of patients with histologically confirmed metastatic melanoma to the brain [Long, 2012]. The IR in patients with no prior local treatment for brain metastases was 39%; in patients with prior local treatment, the IR was 31%.

While the BREAK-MB trial demonstrated activity in patients with active brain metastases, all of the patients in that trial were asymptomatic from CNS disease. Vemurafenib, another elective inhibitor of oncogenic BRAF kinase that specifically targets cancer cells harboring mutated BRAFV600, was recently studied in a cohort of 24 patients with symptomatic brain metastases. Median PFS in the brain was 4.3 months and for other sites was 4.6 months. In addition, an improvement in performance status (decrease from baseline of at least 1 point of ECOG score) was seen in 83.3% of patients, and 66.7% reported a reduction of  $\geq$ 30% (compared with baseline dose) or complete discontinuation of corticosteroids.

This current trial is expected to build upon the current body of evidence of targeted therapy in melanoma brain metastases through an evaluation of the combination of dabrafenib and trametinib in patients with V600-mutation positive melanoma brain metastases.

The alternative hypothesis was selected as the IR that would be clinically relevant for this combination therapy. The study is designed to have 82% statistical power to detect an IR of 50% in V600E mutation-positive subjects who receive dabrafenib in combination with trametinib in Cohort A.

This hypothesis will be tested using a one-sided test for superiority with  $\alpha=0.05$ . There will be no other testing; therefore, there will be no adjustment of the Type I error for multiple testing.

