## 9.2. Study Design Considerations

### 9.2.1. Sample Size Assumptions

The sample size is based on the hypothesized improvement in intracranial response over study GSK BRF113929 (BREAK-MB) in Cohort A. 35% intracranial response (IR) is not clinically significant over existing therapies. An intracranial response (IR) of 50% is of clinical significance.

For the primary endpoint cohort (A), 75 BRAF V600E mutation positive subjects will be enrolled. At the time of the primary efficacy analysis, at least 33 subjects with an IR (44%) are required to establish that the evidence does not support the null hypothesis.

The sample size is based on a one-sided superiority trial of binomial proportions with an overall Type I error rate 0.05 incorporating an interim analysis with alpha-spending function proposed by Lan, 1983 with Pocock Boundary. The null hypothesis in Cohort A

will be tested assuming IR of 35% against an IR of 50% using a one-sided test for superiority with  $\alpha=0.05$  and power=82%. Sample Size Sensitivity

[Table 25](#) shows statistical power for the test of the null hypothesis in Cohort A under the assumed IR of 35% and for scenarios where the alternative response rate is lower and higher, assuming 75 BRAF V600E mutation positive subjects.

Table 25 Statistical Power Scenarios with 75 BRAF V600E Mutation Positive **Subjects in Cohort A**

IR	Statistical Power
40%	22.9%
45%	53.8%
50%	82.1%
55%	96.2%

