### **9.3.5.1. Efficacy Analyses**

#### **9.3.5.1.1. Primary Analysis**

The IR is defined as the percentage of subjects who have a best confirmed intracranial complete or partial response by investigator assessment. Subjects who have an intracranial response of NE (not evaluable) or a missing response will be treated as non-responders, i.e., they will be included in the denominator when calculating the percentage. The primary efficacy analysis will be performed when all subjects in cohort A have had the opportunity for *three (3)* post baseline disease assessments. At least 33 of 75 V600E subjects (44%) must show an intracranial response for the null hypothesis to be rejected. The IR, along with exact two-sided 95% confidence interval, will be reported. Investigator-assessed IR will be considered the primary analysis.

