## 5. SAMPLE SIZE CONSIDERATIONS

### 5.1. Sample Size Assumptions

The sample size is based on the hypothesized improvement in intracranial response over study GSK BRF113929 (BREAK-MB) in Cohort A. A 35% intracranial response (IR) is not clinically significant over existing therapies. An intracranial response (IR) of 50% is of clinical significance.

For the primary endpoint cohort (A), 75 BRAF V600E mutation positive subjects will be enrolled. At the time of the primary efficacy analysis, at least 33 subjects with an IR (44%) are required to establish that the evidence does not support the null hypothesis. The sample size is based on a one-sided superiority test of binomial proportions with an overall Type I error rate 0.05 incorporating an interim analysis with the spending function proposed by Lan,(1983) with Pocock Boundary. The null hypothesis in Cohort A will be tested assuming IR of 35% against an IR of 50% using a one-sided test for superiority with  $\alpha=0.05$  and power=82%. There will be no other testing; therefore, there will be no adjustment of the Type I error for multiple testing and the primary endpoint test in the primary analysis will be performed at 5% level.

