### 5.2. Sample Size Sensitivity

Table 1 shows statistical power for the test of the null hypothesis in Cohort A under the assumed IR of 35%. It includes statistical power for scenarios where the alternative response rate is lower and higher. All statistical power calculations assume 75 BRAF V600E mutation positive subjects in the Cohort A All Treated Subjects population.

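### Does writing the alternative as IR ≥ 50% make a rejection at 33/75 claim more than the test can show?

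*Protocol*

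**What the plan says.** The hypotheses appear in the same form in the Protocol Summary, Protocol 3.1, Protocol 9.1 and SAP 2.1: H0 is IR ≤ 35%, and the study is to support it "or to reject it in favor of the alternative hypothesis", given as IR ≥ 50%, in V600E subjects of Cohort A. Protocol 9.1 adds: "The alternative hypothesis was selected as the IR that would be clinically relevant for this combination therapy". Protocol 9.2.1 says "An intracranial response (IR) of 50% is of clinical significance".

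The operative rule is narrower. Protocol 9.3.5.1.1 states: "At least 33 of 75 V600E subjects (44%) must show an intracranial response for the null hypothesis to be rejected". Protocol 9.2.1 and SAP 5.1 likewise say only that 33 responders count against the null. The test is one-sided at 0.05. An exact two-sided 95% interval is planned in Protocol 9.3.5.1.1, and an exact 95% interval in SAP 11.1.

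Protocol Table 25 and SAP Table 1 give power at 40%, 45%, 50% and 55%. The Protocol introduces its table as being "for scenarios where the alternative response rate is lower and higher", and SAP 5.2 says the same of its own: "It includes statistical power for scenarios where the alternative response rate is lower and higher".

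On the historical study, Protocol 9.2.1 says: "The sample size is based on the hypothesized improvement in intracranial response over study GSK BRF113929 (BREAK-MB) in Cohort A". Protocol 9.3.3 and SAP 7 state that there are no treatment comparisons.

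**The concern.** An alternative normally takes in every rate outside the null. Here 35% to 50% is left uncovered, and the rejection threshold of 44% falls inside that gap. The hypothesis statement attaches rejection to IR ≥ 50%, and the neighbouring sentences attach clinical relevance to that same rate. A reader who took the phrase at its word could report 33/75 as establishing a clinically significant response rate when the observed rate is below it.

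A second strand concerns the historical comparison. The sample size is framed around an improvement over BREAK-MB, whose V600E cohort without prior local therapy had 39.2% (Protocol 1.1.1 and 1.2), while the null is 35%. Rejecting 35% does not exclude 39.2%, so it might be taken to show an improvement over dabrafenib alone that it cannot show.

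At stake is the strength of the conclusion drawn from a single-arm result near the cut-off.

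**Working it through.** **Inputs.** n = 75, null 35%, planning rate 50%, rejection at 33 or more (Protocol 9.2.1, 9.3.5.1.1); continuation if at least 8 of the first 22 respond (Protocol 9.3.4, SAP 4.1); historical rate 39.2% (Protocol 1.1.1).

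**The plan's own power figures.** A one-sample normal approximation with the variance taken at the alternative is

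power = Φ[(p − 0.35)/√(p(1 − p)/75) − 1.645].

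| True IR | Stated power | Normal approximation | Exact P(X ≥ 33) | Exact P(X ≥ 33) with 8/22 binding |
|---|---|---|---|---|
| 40% | 22.9% | 22.3% | 27.6% | 25.3% |
| 45% | 53.8% | 53.8% | 61.3% | 57.3% |
| 50% | 82.1% | 83.0% | 87.6% | 83.9% |
| 55% | 96.2% | 96.7% | 97.9% | 95.9% |

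The approximation comes within one percentage point of every stated value. The exact columns use X ~ Binomial(75, p). The last one treats the 8/22 rule as binding and applies it to the same responses counted at the end. So the printed tables are power for a test against 35%, evaluated at several true rates, with 50% as the planning value.

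**How large the literal gap is.**
- 33/75 = 44.0% and 37/75 = 49.3%; 38/75 = 50.7%. Five rejecting counts (33 to 37) therefore have an observed rate below 50%.
- At 33/75 the exact (Clopper-Pearson) two-sided 95% interval is 32.5% to 55.9%. It contains 35%, 39.2% and 50%.
- At a true IR of 45%, which neither hypothesis covers as written, the rule rejects with probability 61.3% (57.3% gated).
- At a true IR of 39.2%, P(X ≥ 33) = 23.1% (21.1% gated). This treats 39.2% as fixed; the documents give neither that cohort's size nor whether its responses were confirmed.

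**What these numbers mean.** A test with more than 50% power at its planning rate will ordinarily have its cut-off below that rate, so rejecting counts under 50% are not in themselves a fault. The 23.1% is power against a 35% null at one point above it, and Table 25 already discloses 22.9% at 40%.

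**Phrase against rule.**
- Hypothesis statement: rejection is in favour of IR ≥ 50%.
- Decision sentences: rejection concerns the null only.
- Power tables: 40% and 45% are treated as alternative response rates, so the working alternative is any rate above 35%.
- BREAK-MB: the improvement is called hypothesized, and comparisons are ruled out.

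Nothing downstream uses the literal first line.

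**A limit on substitute wording.** The exact P(X ≥ 33) at 35% is 0.0668 (0.0602 with 8/22 binding), against the stated 0.05. With a cut-off of 34 it is 0.0414 ungated. At 33/75 the one-sided 95% lower bound is 34.2%. A sentence saying that rejection establishes IR > 35% would therefore itself overstate a result of exactly 33/75 at exact one-sided 5%. The size of the test is a separate matter from how the alternative is written.

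**The case for a change.** The strongest case for acting is that shorthand is harmless only where another sentence says what rejection means. Here the adjacent sentences instead attach clinical relevance to the 50% rate. The phrase occurs in four places, the gap is 15 percentage points wide, and with no control arm the wording of the conclusion carries weight. Correcting it costs a few words.

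Much of that stands. The written alternative is not the complement of the null, and writing it as IR > 35% with 50% named as the planning alternative would be tidier. What does not stand is the consequence. No section says that rejection establishes 50%; the clinical-relevance sentences explain why 50% was chosen for powering. A result of 33/75 would be reported as 44% with an interval of 32.5% to 55.9%, which shows directly that 50% has not been established.

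The dabrafenib strand is weaker. The plan already calls the improvement hypothesized and excludes treatment comparisons, so a disclaimer would repeat what is there.

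**Conclusion.** The mismatch is real but confined to wording, and no change to the plan follows. Two statisticians following the documents would apply the same rule, make the same decision and report the same estimate and interval whichever way the alternative is written. Rewording would alter neither the 75 subjects, the 35% null, the 33/75 rule, the power table nor any analysis.

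This rests on the decision sentences in Protocol 9.2.1 and 9.3.5.1.1 governing the conclusion, and on the exact interval being reported beside it, as planned. The conclusion covers only how the alternative is stated. It does not endorse the 33/75 cut-off, whose exact type I error is 0.067 (0.060 with a binding interim rule).
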